#### **10. Reasons for participant withdrawal from the one year clinical trial**

If any of the male patients develop any of the following adverse events, the patient will be withdrawn from the one year trial:

- Severe hypoglycemia defined as blood glucose of less than 50 on more than one occasion
- Diagnosis of intracranial hypertension
- Diagnosis of SCFE (slipped capital femoral epiphysis)
- Diagnosis of malignant neoplasia

If withdrawn from the 1 year trial treatment, the patient will remain in the phenotypic data collection aspect of the trial, and measures as described in Table 1 and Figure 2 for the 12 month/1 year time point will be conducted as scheduled.

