## 4. Study Design and Methods.

Our study is divided in to three different parts:

- 24-hour pharmacokinetic response of free and total IGF-1 and IGF binding protein-3 (IGFBP-3) to a single dose of rhIGF-1 (120 mcg/kg) in three patients with PAPP-A2 mutation compared to up to four unaffected heterozygous relatives and 2 healthy adult controls. This part is complete.

- One-year trial of rhIGF-1 at standard dose given to the two youngest males with PAPP-A2 mutation. The primary end point of this trial will be first year height velocity. Secondary outcomes will include change in height SDS, change in height velocity SDS, and change in whole body and lumbar spine bone mineral density. This part is complete, and will be followed by an extension part. Provided continued improved height velocity (defined as height velocity at the 25th percentile or better) without adverse effects, treatment with IGF-1 will be continued on an annual basis until closure of the growth plates indicating achievement of near-adult or adult height (bone age  $\geq$  15 years or 17 years, respectively, for males).

- Description of additional phenotypic characteristics of patients with PAPP-A2 mutation by studying glucose and insulin metabolism, body composition, bone geometry and bone density before and after treatment with rhIGF-1. This part will be complete in 2019 for the subjects not on Increlex.

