Following the initial PK study at CCHMC, the patients will then undergo a one-year treatment trial with rhIGF-1 which will be started at 60 mcg/kg BID SC given twice daily for one week. If well tolerated, the IGF-I will be increased to 120 mcg/kg BID SC and the patients will be maintained at this dosage for one year. Doses will be given within 20 minutes of eating breakfast and dinner. Tolerability will be determined with frequent blood glucose measurements via finger stick. The patients will be instructed to measure their blood glucose 3 times per day: fasting, between 10:00-12:00 h, and between 20:00-22:00 h. In addition, they will keep a daily log which we will review via telephone or e-mail. Once the dose is increased to 120 mcg BID, they will continue to measure their blood glucose for one additional week. If no significant episodes of hypoglycemia occur, then they can continue to measure their blood glucose only as needed for symptoms of hypoglycemia. If hypoglycemia dose occur, the parents will be instructed to treat the patient with fast acting carbohydrates (such as juice) and to recheck the blood sugar in 15 minutes as we do with our patients with type 1 diabetes.

They will be re-evaluated as outpatients after 3 months, 6 months, 9 months and 12 months of treatment for serial height measurements and for close monitoring of possible side effects. The dose of rhIGF-I will be adjusted for weight at each of these visits. ECG will be performed at baseline and at each of the study visits. Echocardiogram will be performed at the 6 month and 12 month visit. A funduscopic, oropharyngeal, back and hip exam will be performed at baseline and during each of the study visits. A glucometer and testing strips will be provided for home monitoring of blood glucose concentration. We will have monthly follow up calls with the family to assess for any complications. In addition, we will be in close contact with the patient's primary care provider and local endocrinologist who will receive a detailed letter after each of the follow up visits. If any unexpected issues arise we will help coordinate prompt follow up with PCP or with local endocrinologist.

Study drug is being donated by Ipsen (the drug manufacturer) and will be provided to the patients by the study team at no cost.

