**Dosage Interruption** – In the event that either participant experiences a dosage interruption of >48 consecutive hours during the one year trial, the participant will be restarted at a dose of 60 mcg/kg BID SC given twice daily for one week. If well tolerated, the IGF-I will be increased to 120 mcg/kg BID SC and the patient will be maintained at this dosage for the remainder of the one year trial.

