- Development of malignant neoplasia: If malignant neoplasia develops in any patients receiving Increlex therapy, treatment will be immediately discontinued and the patient will be referred for the appropriate medical care.

In addition, we will be in close contact with the patient's primary care provider and local endocrinologist who will receive a detailed letter after each of the follow up visits. If any unexpected issues arise we will help coordinate prompt follow up with PCP or with local endocrinologist.

**Injection site reactions:** The patients can experience local symptoms related to the subcutaneous administration of rhIGF-1 which include pain at the site of the injection, redness, small bruising, lipoatrophy or lipohypertrophy. Injection site reactions can be avoided by changing the injection site at each injection (injection site rotation).

**Immunogenicity:** There is a risk of potential development of antibodies to administered rhIGF-1. Blood samples will be taken at baseline, periodically and at the end of the study to monitor the potential generation of antibodies.

**Radiation risk:** Every person is exposed on a daily basis to a certain amount of background radiation originating from soil, rocks, outer space and within the body itself. The amount of radiation for imaging studies varies based on the size of the patient, with children and smaller adolescents being exposed to relatively larger doses of radiation than adults. The average person in Cincinnati receives a radiation dose of about 3 mSv per year. Using the largest exposure estimates for children, the proposed radiology studies would expose the patients to the following amounts of radiation:

- DXA scan (total body, lumbar spine, hip and forearm): 0.013 mSv; two DXA scans: 0.027 mSv
- peripheral QCT: less than 0.01 mSv; two peripheral QCT: less than 0.02 mSv
- Bone age (X-ray of the hand): 0.005 mSv; two bone age studies: 0.01 mSv

Therefore, total radiation exposure from this study is expected to be 0.05 mSv or less (equivalent to the amount an individual receives over 6 days from background radiation).

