### **2. Study protocol:**

This is an extension trial of rhIGF-1 at a standard dose given to one subject (youngest affected male) with PAPP-A2 gene mutation who has benefited from previous treatment. The primary outcome measures of interest are height velocity and change in height standard deviation scores (Ht SDS). Our patient will continue to receive twice daily SC injections with rhIGF-1 (Increlex®) at a standard dose of 120 mcg/kg/dose. Additionally, there will be ongoing phenotyping which will be performed in all affected siblings at the yearly study visits.

The parents have been previously trained on glucometer use which they have available to be used as needed for signs and symptoms of hypoglycemia. If hypoglycemia does occur, the parents have been instructed to treat the patient with fast acting carbohydrates (such as juice) and recheck the blood glucose in 15 minutes.

For monitoring, the patient will come to the CCHMC CTRC for a series of outpatient research visits every 4 months during the second year of treatment, and every 6 months for subsequent years of treatment. The lab and assessment schedule is detailed below. At each study visit, we will obtain a height in triplicate (cm) and weight (kg) measured using a wall-mounted Harpenden stadiometer and electronic scale respectively. Additionally, fasting blood samples will be obtained. The patient will be evaluated as an outpatient at 16 months, 20 months, 24 months and every 6 months thereafter for serial height measurements and for monitoring of possible side effects. Each visit has a +/- 2 week window to allow for travel schedules. The dose of rhIGF-I will be adjusted for weight at each of these visits. A funduscopic, oropharyngeal, back and hip exam will be performed during each of the study visits. The family will be instructed to call us in-between study visits should any adverse reactions occur. In addition, we will be in close contact with the patient's primary care provider and local endocrinologist who will receive a detailed letter after each of the follow up visits. If any unexpected issues arise we will help coordinate prompt follow up with PCP or with local endocrinologist. Study drug is being donated by Ipsen (the drug manufacturer) and will be provided to the patients by the study team at no cost.

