#### **6. Investigators (Extension trial):**

[name] (Principal Investigator), [name] (Co-Principal Investigator), [name] (Coordinator for the CCGD), [name] (Fellow), [name] (Co-Investigator), [name] (Co-investigator).

**7. Study consents:** An additional written extension consent and assent will be obtained. See separate document.

**8. Risks/ Benefits:** These are unchanged.

**9. Reasons for premature termination of the clinical trial:** These are unchanged.

**10. Reasons for completion of the clinical trial:** When it has become clear that the participant receiving rhIGF1 therapy has finished growing, the treatment arm of the study will be stopped. This is defined by either of the following:

- The participant reaching full skeletal maturity with a bone age of 17 years, or  $\geq 15.5$  years, and:
- The participant's height velocity is  $< 2$ cm per year

Once the decision has been made to discontinue treatment, all three affected siblings will be asked to return for one more phenotyping visit a year (+/- 2 weeks) from the date that treatment was stopped. The study labs and assessments will be the same as previous phenotyping visits with the exception of those that are completed as a result of rhIGF1 exposure (i.e. antibody, ECG, renal/spleen ultrasound).

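### The visible hypoglycemia stopping rule needs glucose below 50 more than once, so one episode with seizure or loss of consciousness triggers no written hold or review for the boy still treated

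*Combined protocol and SAP*

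**What the plan says.** Section 10 of the main protocol lists four reasons for withdrawing a treated boy. The one for hypoglycemia is "Severe hypoglycemia defined as blood glucose of less than 50 on more than one occasion". The other three are diagnoses: intracranial hypertension, slipped capital femoral epiphysis and malignant neoplasia.

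The year-1 treatment part is over: section 4 says "This part is complete, and will be followed by an extension part". The extension treats one boy at 120 mcg/kg twice daily. Its stopping text is one line: "9. Reasons for premature termination of the clinical trial: These are unchanged".

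For an episode of hypoglycemia, the extension's Study protocol section says "the parents have been instructed to treat the patient with fast acting carbohydrates (such as juice) and recheck the blood glucose in 15 minutes". It also says "The family will be instructed to call us in-between study visits should any adverse reactions occur", and offers help in arranging follow-up with local physicians if something unexpected arises.

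Section 4.2 has a half-dose restart step, limited to a "dosage interruption of >48 consecutive hours during the one year trial". For malignancy, section 9 is explicit: "treatment will be immediately discontinued and the patient will be referred for the appropriate medical care".

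**The concern.** Hypoglycemia is the first side effect that section 9 lists, and the boy is to be injected twice a day until he stops growing. The hypoglycemia criterion depends on a repeated meter reading and has no clinical component. After a seizure, a parent or local physician may be the first to respond, and the next injection falls due at the next of two daily dosing times. The visible plan does not say whether to give that injection, that the investigator must review the case first, or at what dose to resume. The stated first aid also assumes a child who can swallow safely.

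At stake are this boy's safety and, to a lesser degree, consistent handling of events under the extension's long-term safety and tolerability objective.

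**Working it through.** The plan gives no figure to reproduce here. The check applies the rule to cases, then looks for other text that would fill the gap.

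**Step 1. Apply the rule.** Withdrawal is required if the number of occasions with glucose below 50 is at least 2. Two assumptions: the unit is mg/dL (none is given), and the 15-minute recheck belongs to the same occasion as the reading before it.

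| Case | Occasions below 50 | Withdrawal required? |
|---|---|---|
| One seizure or loss of consciousness, reading below 50 | 1 | No |
| The same, no reading taken | 0 | No |
| The same, first reading after treatment is 50 or above | 0 | No |
| Two symptom-free readings of 49 on separate occasions | 2 | Yes |

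The order is wrong for safety: the mildest case is the only one that triggers action. If a recheck counted as a separate occasion, the first case could qualify, but only if the recheck was also below 50. The second and third cases would still not qualify. After the initial weeks, glucose is measured only when symptoms prompt it, so the rule relies on someone using a meter during an emergency.

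**Step 2. Look for other text on the next dose.**

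- Extension, Study protocol: oral carbohydrate, a recheck and a call to the team. Nothing on the next injection.
- Section 2 (specific aims) and section 4: treatment beyond the first year depends on tolerability, and annual renewal on growth without adverse effects. Neither passage defines the event or gives a hold or restart step.
- Section 4.2, titration: the increase to 120 mcg/kg depends on tolerability. No action is stated if the starting dose is not tolerated.
- Section 4.2, dosage interruption: says how to resume after a long gap, not what should cause one, and is confined to year 1.
- Section 9: an explicit immediate stop for malignancy. Its hypoglycemia entry covers monitoring only.

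None of these tells the family or a local physician what to do about the next dose.

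**Step 3. Cost of a hold with a half-dose restart.** Doses are from section 4.2; hold lengths are assumptions.

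- Full-dose day: 2 × 120 = 240 mcg/kg.
- Restart week: 7 × 2 × 60 = 840 mcg/kg, against 7 × 2 × 120 = 1680 mcg/kg at full dose.
- Loss in that week: 1680 − 840 = 840 mcg/kg; 840 / 240 = 3.5 full-dose days.

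| Assumed hold | Full-dose days lost | Share of a year's drug |
|---|---|---|
| 3 days | 3 + 3.5 = 6.5 | 6.5 / 365 = 1.8% |
| 7 days | 7 + 3.5 = 10.5 | 10.5 / 365 = 2.9% |
| 14 days | 14 + 3.5 = 17.5 | 17.5 / 365 = 4.8% |

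**The case against.** The strongest reply is that section 10 says when withdrawal is compulsory and was never meant to be the whole safety plan. The investigator may stop earlier. The family is told to call about adverse reactions, so a seizure would very probably reach the team that supplies the drug. Renewal of treatment is conditional on no adverse effects. This stands, and it limits the point. A reader might infer that the plan requires dosing to continue after a seizure, or that no safeguard exists. The documents support neither. What remains is that a call is not a dosing instruction, and the next dose may fall due before anyone has decided.

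A second reply is that this is a claim of absence made on incomplete text. Sections 6 and 8 and the openings of both the main protocol and the extension were not available for this review. Section 4.2 also invokes the FDA-approved regimen, whose content is not in the documents. That stands too: the point covers visible text only, and the sponsor should check those places.

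Third, the carry-over is an inference. Section 10 speaks of participant withdrawal, item 9 of premature termination of the trial. No other visible list fits item 9. If section 10 did not carry over, the visible extension would have no hypoglycemia stopping criterion at all.

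Fourth, year 1 promised "We will have monthly follow up calls with the family to assess for any complications" and the extension relies on the family to call. A reader might infer that sparser scheduled contact measures the added risk. It does not: a seizure would prompt a call under any visit schedule.

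**Conclusion.** The concern holds for the visible text. The only hypoglycemia stopping criterion misses a single clinically severe episode, and nothing visible says whether the next dose is given. The amendment is worth making because the criterion ranks events in the wrong order for safety and the correction costs little.

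The scope is small: one boy, in the extension only, since the year-1 treatment part is complete. The documents give no frequency for hypoglycemic seizure, so expected harm cannot be sized, and he enters the extension having already benefited from treatment. Section 7 describes the treatment study as descriptive, so no estimate, test or conclusion changes.

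A reader might go further and infer that one unexplained episode should end treatment, or that only one restart should be allowed. The documents give no basis for either. In a single-patient extension, that decision belongs to the investigator.

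The conclusion assumes that item 9 imports section 10, that readings within one treated episode form one occasion, and that the unavailable sections contain no hold rule. Confidence is moderate, mainly because of the last.

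**What to change.** Keep the existing criterion. Add to item 9 of the extension:

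> After any single episode of suspected hypoglycemia with seizure or loss of consciousness, whatever the meter reading or if none was taken, rhIGF-1 is held and the investigator reviews the case before any further dose. The investigator decides on restart or withdrawal; any restart uses 60 mcg/kg twice daily for one week, then 120 mcg/kg twice daily if well tolerated.

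Add to the family instructions in the extension's Study protocol section:

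> If he cannot safely drink, give nothing by mouth and call emergency services; give no further rhIGF-1 and call the study team the same day.

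The restart reuses the protocol's own two-step dose. The word 'suspected' means nobody has to prove low glucose before holding, so a faint or an unrelated seizure may also lead to a hold; investigator review then settles it.

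The cost is two short text changes and, for each event, one call and one review, plus whatever evaluation the investigator considers necessary. No scheduled visit or test is added. The downside is the brief treatment interruption worked out above.

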#### **11. IND Status**

This study will be performed under an IND from the FDA.

## **2. Main Objective and secondary objectives:**

### **Main objective:**

- To provide ongoing treatment with rhIGF-1 (Increlex®) to our patient who has benefited from previous treatment (as detailed in the preliminary results section) and to closely monitor his continued response to treatment.

### **Secondary objectives:**

- Assess the long-term safety and tolerability of rhIGF-1 in one subject with PAPP-A2 gene mutation
- Describe the evolution of several metabolic parameters including glucose handling, body composition, and bone mineral density in the three affected siblings with PAPPA2 gene mutation.

## **3. Study design and methods:**

**Subject recruitment:** No additional participants will be recruited for this extension protocol.

### **2. Study protocol:**

This is an extension trial of rhIGF-1 at a standard dose given to one subject (youngest affected male) with PAPP-A2 gene mutation who has benefited from previous treatment. The primary outcome measures of interest are height velocity and change in height standard deviation scores (Ht SDS). Our patient will continue to receive twice daily SC injections with rhIGF-1 (Increlex®) at a standard dose of 120 mcg/kg/dose. Additionally, there will be ongoing phenotyping which will be performed in all affected siblings at the yearly study visits.

The parents have been previously trained on glucometer use which they have available to be used as needed for signs and symptoms of hypoglycemia. If hypoglycemia does occur, the parents have been instructed to treat the patient with fast acting carbohydrates (such as juice) and recheck the blood glucose in 15 minutes.

For monitoring, the patient will come to the CCHMC CTRC for a series of outpatient research visits every 4 months during the second year of treatment, and every 6 months for subsequent years of treatment. The lab and assessment schedule is detailed below. At each study visit, we will obtain a height in triplicate (cm) and weight (kg) measured using a wall-mounted Harpenden stadiometer and electronic scale respectively. Additionally, fasting blood samples will be obtained. The patient will be evaluated as an outpatient at 16 months, 20 months, 24 months and every 6 months thereafter for serial height measurements and for monitoring of possible side effects. Each visit has a +/- 2 week window to allow for travel schedules. The dose of rhIGF-I will be adjusted for weight at each of these visits. A funduscopic, oropharyngeal, back and hip exam will be performed during each of the study visits. The family will be instructed to call us in-between study visits should any adverse reactions occur. In addition, we will be in close contact with the patient's primary care provider and local endocrinologist who will receive a detailed letter after each of the follow up visits. If any unexpected issues arise we will help coordinate prompt follow up with PCP or with local endocrinologist. Study drug is being donated by Ipsen (the drug manufacturer) and will be provided to the patients by the study team at no cost.

The three affected siblings (two males, one female), will be assessed at the yearly outpatient study visits for further phenotyping. During this visit, we will obtain fasting blood samples in addition to the following tests:

- Oral glucose tolerance test (OGTT)
- Dual energy-x-ray absorptiometry (DXA) scan of whole body, lumbar spine, hip and forearm.
- The two affected brothers that are still growing will get a repeat bone age x-ray.
- The affected younger brother on rhIGF-I treatment will have an electrocardiogram, and repeat renal and spleen ultrasounds. (Please refer to the original protocol for full details).

These tests were all done at baseline and at the end of the first year of the trial as well. Since this has already been approved, we have not included it in the extension trial application or protocol.

#### **Lab and assessment schedule:**

Lab	16 month	20 month	24 month	Monitoring (30, 42, 54 etc. month)	Yearly Phenotyping (36, 48, 60 etc. month)
			Year 2 of Treatment		Year 3+ of Treatment
CBC			X		X
Metabolic Panel	X	X	X	X	X
Lipid Profile			X		X
Whole Blood			X		X
A1C	X	x	X	X	X
Insulin	X	X	X	X	X
Glucose	X	X	X	X	X
GH	X	X	X	X	X
IGF-I	X	X	X	X	X
IGFBP-3	X	X	X	X	X

ALS	X	X	X	X
Free IGF-I	X	X	X	X
PAPP A2	X	X	X	X
rhIGF-I Antibodies	X	X	X**	X
Osteocalcin			X	X
C-telopeptide			X	X
Vitamin D			X	X
Phosphorus			X	X
Free fatty acids			X	X
Additional Testing:				
ECG			X**	X**
OGTT			X	X
DXA scan			X	X
Bone age			X*	X*
Renal US			X**	X**
Spleen US			X**	X**

\*This testing will be obtained on participants that are still growing

\*\* This testing will be obtained only for participants on rhIGF-I treatment

